#### **4.3.5. Physical Examination Findings**

A complete physical examination will be conducted at Screening and targeted physical exams will be conducted at every visit from Day 1 through Day 99 (14 weeks). Physical examination findings at each scheduled visit will be summarized overall for all subjects in the SAF Population. The number and percent of subjects with abnormal findings by body system will be tabulated.

#### **4.3.6. Medications and Procedures**

All prescriptions or over-the-counter medications continued at the start of the trial or started during the trial, and different from the study drug will be recorded. All of these medications will be coded using WHO Drug Dictionary (March 2019). The use of another version will not be considered a violation of the SAP, nor require an amendment to the plan. Both the coded terms and verbatim terms will be presented in data listings for:

- Concomitant procedures (procedures are not coded)
- Previous and Concomitant medications
- ART medications – only for HIV infected subjects

#### **4.4. Questionnaires**

[figure not shown]
Participants in the IM Group will be asked to complete questionnaires to assess their satisfaction with the different modes of Trogarzo® administration. HIV infected participants in the IM Group will complete the HIVTSQ status version (HIVTSQs12) at Day 29 regarding IVI administration and at Day 85 regarding IM administration. In addition, they will also complete the change version of the questionnaire (HIVTSQc12) following completion of the IM portion of the study (Day 85). HIV uninfected participants will complete the SMSQ status version (SMSQs) at Day 29 regarding IVI administration and at Day 85 regarding IM administration. In addition, they will also complete the change version of the questionnaire (SMSQc) following completion of the IM portion of the study (Day 85). Instructions and questionnaires are provided in Appendix D of the protocol. Summary statistics by visit will be presented for all subjects who answered each question. Paired results of the HIVTSQs12 at Day 85 vs Day 29, and paired results of the SMSQs at Day 85 vs Day 29, will be compared using the Wilcoxon signed-rank test.

All subjects will also be asked to answer the following one-question Preference Assessment (not associated with the above questionnaires) at Day 85: “For the past 8 weeks you have received IM injections every 2 weeks. Today we would like you to compare your experience on the IM injections with the IV infusion you received previously during this study. Which type of administration do you prefer?”. Results will be presented in a frequency table summarizing the incidence of each possible answer.

#### **4.5. PK**

The PK endpoints are to compare the trough serum drug concentration and AUC after IV Infusion with the diluted drug to the trough concentration and AUC after IM injection with the undiluted drug. Serum concentrations will be used to estimate PK parameters. PK parameters will be estimated for all subjects by non-compartmental analysis of the serum concentration-time data. Missing data will not be imputed. The trough concentrations and AUC for IM injection and IV infusions over 15 minutes will be

estimated. The following graphic illustrates the time points at which the  $C_{trough}$  and AUC values will be estimated.

The  $C_{trough}$  values for all IM injection and all IV infusions over 15 minutes will be estimated. A PK bridge will be demonstrated if the proportion of subjects with mean  $C_{trough}$  equal to or exceeding the threshold of 300 ng/mL are comparable for IV infusion over 15 minutes to IM injection. Both the geometric and arithmetic mean  $C_{trough}$  will be calculated and analysis results will be presented for both means. Analysis will be conducted by pooling all the  $C_{trough}$  measurements into two groups (IVI=Reference; IMTest) and dichotomizing the  $C_{trough}$  data ( $< 300$  ng/mL=1;  $\geq 300$  ng/mL=0). Fisher's exact test for comparing two independent binomial proportions will be conducted initially to test for equality of the proportions. In a subsequent test, the PK bridge will be based on relative risk assuming that the binary data in the two infusion groups are independent samples. Two one-sided tests of significance (TOST) will be carried out for the pair of hypotheses,  $H_{0a}: \rho \leq \rho_0$  versus  $H_{1a}: \rho > \rho_0$  and  $H_{0b}: \rho \geq \rho_1$  versus  $H_{1b}: \rho < \rho_1$ . Rejection of both  $H_{0a}$  and  $H_{0b}$  would mean that the relative risk lies in the zone of equivalence. The syntax below will be used in SAS to carry out the score test with  $\rho_0 = 0.8$ , and  $\rho_1 = 1.25$ .

```
proc freq data=<filename> order=data;
tables group*Cthrough/relrisk(equivalence margin=(.80, 1.25)
method=FM);
weight count;
format Cthrough Cthrough.;
run;
```

Details of reported outputs from the analysis will be displayed in the mock tables and will include relative risk, equivalence limits, 90% confidence limits, and TOST p-values of lower margin, upper margin, and overall. Missing data will not be imputed or used in the analysis. In addition, the two-tailed p-value from Fisher's exact test will be presented to provide additional supporting evidence for equality of binomial proportions between the two administrative routes in the Ctrough cutoff at 300 ng/mL.

A 90% confidence interval of log transform of the ratio of the geometric means for IM injection to IV infusion will be calculated. Additionally, the PK bridge between the IM injection and IV infusion is demonstrated for AUC if the 90% confidence interval of log transform of the ratio of the geometric means for IM injection (test product) to IV infusion (reference product) for the 20 subjects in the study is within a 80%-125% criteria.

In accordance with the FDA Guidance (2001) [2], SAS PROC MIXED will be used to fit a factor-analytic variance-covariance structure using the FA0(2) option to the ln-transformed AUC data by subject, group (HIV+ or HIV-), PK period, and infusion type (IVI=Reference; IM=Test) to estimate 80%-125% criteria. For each type of administration, subject-level AUC data will be labeled as PK Period 1 or PK Period 2 corresponding to the graphic above. Unless a subject has missing data for both administration routes and both periods, the subject's data will be included in the analysis because SAS PROC MIXED can handle missing data. Details of reported outputs from the analysis will be displayed in the mock tables and will include mean estimate and its lower and upper bounds.

The following SAS code syntax will be used to calculate estimates:

```
proc mixed data=lnauc method=reml;
  class infusiontype population period ;
  model lnauc= population period infusiontype/ddf=kenwardroger;
  random infusiontype /type=FA0(2) subject=subject;
  repeated/group=infusiontype subject=subject;
  estimate 'T-R' infusiontype 1 -1/CL alpha=0.1;
  ods output estimates=test;
  data test;
  set test;
  meanrat= exp (estimate); * Estimated mean ratio on original scale;
  lowerb=exp(lower); * Lower bound on original scale;
  upperb=exp(upper); * Upper bound on original scale;
  proc print data=test noobs;
  var meanrat lowerb upperb;
  run;
```

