## 9.7 Pharmacokinetic Analyses

Serum concentrations will be used to estimate PK parameters. PK parameters will be estimated for all subjects by noncompartmental analysis of the serum concentration-time data. Missing data will not be imputed. For the re-enrolled participants, the PK parameters of IVI and IM will be estimated from their first enrollment and second enrollment, respectively. The exposure-response relationship established for the review of the ibalizumab Biologics License Application (BLA) was based on  $C_{trough}$ , rather than AUC.  $C_{trough}$  was used as an indicator of exposure and a clear trend between exposure and the efficacy endpoint was observed. Therefore,  $C_{trough}$  is more representative of efficacy for this pharmacokinetic bridging study than AUC. A PK bridge between the IV push and IVI and between the IM injection and IVI is demonstrated if the proportions of subjects with average  $C_{trough}$  equal to or exceeding the threshold of 300 ng/mL are comparable using a Fisher's Exact test. A PK bridge is also demonstrated for AUC if the 90% confidence interval of log transform of the ratio of the geometric means for IV push or IM injection (test product) to IVI (reference product) for the 40 subjects in the study is within the 80%-125% criteria.

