## 2.2. Study Objectives

### 2.2.1. Primary

The primary objectives of the IM portion of this study are to:

- Evaluate the safety of Trogarzo® administered by IM injection in clinically-stable human immunodeficiency virus type-1 (HIV-1) infected subjects with at least 3 months of stable treatment with a Trogarzo®-containing antiretroviral (ARV) regimen or healthy HIV uninfected volunteers
- Compare the trough serum drug concentration after IVI with the diluted drug to the trough serum concentration after IM injection of undiluted Trogarzo®

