## **2.2. Study Objectives**

### **2.2.1. Primary**

The primary objectives of this study are to:

- Evaluate the safety of Trogarzo® administered as an undiluted IV push over 30 seconds in clinically-stable human immunodeficiency virus type-1 (HIV-1) infected subjects with at least 3 months of stable treatment with a Trogarzo®-containing antiretroviral (ARV) regimen or healthy HIV-uninfected volunteers
- Compare the AUC and trough serum drug concentration after IV infusion with the diluted drug to the AUC and trough concentration after IV push with the undiluted drug

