  run;
```

The  $C_{trough}$  values for all IV push and all IV infusions over 15 minutes will be estimated. Additionally, the PK bridge will be demonstrated if the proportion of subjects with average  $C_{trough}$  equal to or exceeding the threshold of 300 ng/mL are comparable for IV infusion over 15 minutes to IV push over 30 seconds. Analysis will be conducted by pooling all the  $C_{trough}$  measurements into two groups (IVI=Reference; IVP=Test) and dichotomizing the  $C_{trough}$  data ( $< 300$  ng/mL=1;  $\geq 300$  ng/mL=0). Fisher's exact test for comparing two independent binomial proportions will be conducted initially to test for equality of the proportions. In a subsequent test, the PK bridge will be based on relative risk assuming that the binary data in the two infusion groups are independent samples. Two one-sided tests of significance (TOST) will be carried out for the pair of hypotheses,  $H_{0a}: \rho \leq \rho_0$  versus  $H_{1a}: \rho > \rho_0$  and  $H_{0b}: \rho \geq \rho_1$  versus  $H_{1b}: \rho < \rho_1$ . Rejection of both  $H_{0a}$  and  $H_{0b}$  would mean that the relative risk lies in the zone of equivalence. The syntax below will be used in SAS to carry out the score test with  $\rho_0 = 0.8$ , and  $\rho_1 = 1.25$ .

```
proc freq data=<filename> order=data;
  tables group*Ctrough/relrisk(equivalence margin=(.80, 1.25)
  method=FM);
  weight count;
  format Ctrough Ctrough. ;
  run;
```

Details of reported outputs from the analysis will be displayed in the mock tables and will include relative risk, equivalence limits, 90% confidence limits, and TOST p-values of lower margin, upper margin, and overall. Missing data will not be imputed or used in the analysis. In addition, the two-tailed p-value from Fisher's exact test will be presented to provide additional supporting evidence for equality of binomial proportions between the two administrative routes in the  $C_{trough}$  cutoff at 300 ng/mL.

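### The primary trough comparison is planned only as a count at 300 ng/mL; no code or table estimates a trough ratio, so the trough criterion can be met despite a large fall

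*SAP*

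**What the plan says.** **Objective.** The IM SAP (2.2.1) lists as primary: "Compare the trough serum drug concentration after IVI with the diluted drug to the trough serum concentration after IM injection of undiluted Trogarzo". The IV push SAP (2.2.1) lists: "Compare the AUC and trough serum drug concentration after IV infusion with the diluted drug to the AUC and trough concentration after IV push". The protocol synopsis (Statistical Considerations) says AUC and trough will be compared within subjects. Protocol 9.7 calls Ctrough more representative of efficacy than AUC.

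**Decision rule.** Protocol 9.7 accepts a bridge if the proportions of subjects with average trough "equal to or exceeding the threshold of 300 ng/mL are comparable using a Fisher's Exact test". The IM SAP (4.5) states: "A PK bridge will be demonstrated if the proportion of subjects with mean" trough at or above the threshold is comparable for the two routes. There, "Fisher's exact test for comparing two independent binomial proportions will be conducted initially to test for equality of the proportions". A relative-risk equivalence test (TOST) follows, coded as "relrisk(equivalence margin=(.80, 1.25)". The IV push SAP (4.4) introduces its rule with "Additionally, the PK bridge will be demonstrated if the proportion of subjects with average" and applies the same two tests, "assuming that the binary data in the two infusion groups are independent samples".

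**Planned output.** The trough shells (IM mock Tables 14.2.1 and 14.2.2; IV push mock Table 14.2.2) hold only proportions, the relative risk with its 90% limits, and p-values. The geometric and arithmetic means in IM SAP 4.5 are per-subject averages that are then cut at 300 ng/mL. The only coded ratio model has ln(AUC) as its response, and its shells are titled AUC. One sentence in IM SAP 4.5 promises a 90% CI for a ratio of geometric means without naming the parameter; no code or shell applies it to trough.

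**The concern.** The objective asks how the concentration changes; the analysis asks only whether a subject is on the right side of a cut-off. Subjects well above 300 ng/mL can lose much of their trough and count as unchanged. With 20 subjects per route, few have to cross the line even when every trough falls.

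The data that answer the objective, paired infusion and test-route troughs in the same subject, are collected but not modelled. AUC gets a ln-scale mixed model, while the parameter the protocol ranks above it for efficacy does not. A bridge conclusion could rest on the threshold count with no estimate of the trough change beside it.

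**Working it through.** **The plan's own figure.** Protocol 9.8 says 20 per route gives 80% power. A paired equivalence test on ln(AUC) with limits 0.80–1.25, one AUC per route, true ratio 1.0 and n = 20 has power 82.3% at the stated maximum within-subject CV of 23%, and 86.2% at 22%. So the figure is reproducible for AUC. No power statement covers the trough proportion.

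**A case that needs no simulation.** Suppose all 20 infusion troughs are at least 600 ng/mL and the new route halves each one. All stay at or above 300, so the table is 20/20 against 20/20 and Fisher p = 1.0. The score test uses z = (p1 − r0·p2) / √[p̃1(1−p̃1)/n + r0²·p̃2(1−p̃2)/n], where p̃ are the estimates restricted to p̃1 = r0·p̃2.
- Lower margin, r0 = 0.8: p̃1 = 0.8, p̃2 = 1, so z = 0.2/√0.008 = 2.236 and p = 0.013.
- Upper margin, r0 = 1.25: p̃1 = 1, p̃2 = 0.8, so z = −0.25/√0.0125 = −2.236 and p = 0.013.

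Equivalence is declared at a true trough ratio of 0.5. It is also declared at 19/20 against 20/20 (p = 0.047 on the lower side), but not at 18/20 (p = 0.13). Fisher reaches p < 0.05 only when 20/20 falls to 15/20 (p = 0.047; at 16/20, p = 0.106). I used the proportion at or above 300 ng/mL, as the shells label it.

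**How often it happens.** The documents give no trough variability, so these are assumptions:
- n = 20; two infusion and four IM troughs per subject, averaged geometrically; lognormal troughs.
- Within-subject trough CV 30–60%; the same ratio in every subject.
- Between-subject ln-SD (s) 1.0–2.07. The upper value fits the earlier IM data in Protocol 1.3 (63% above 0.3 µg/mL, mean 5.1 µg/mL): s²/2 + 0.332s = ln(5.1/0.3) = 2.833, so s = 2.07.

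If p is the infusion share at or above 300 ng/mL, halving gives a share of Φ(Φ⁻¹(p) − 0.693/s). At p = 90% this is Φ(1.282 − 0.693) = 72% for s = 1.0 and Φ(1.282 − 0.335) = 83% for s = 2.07.

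| Infusion share ≥300 ng/mL | TOST passes a true halving |
|---|---|
| 95% | about 14–52% |
| 90% | about 3–19% |
| 80% | about 0–2% |
| 63% | 0% |

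Across these settings Fisher is non-significant in about 81–100% of trials. Failure of TOST at low shares does not mean that it has detected the fall: at a 63% share (s = 2.07, one trough per route, CV 23%) it passes only about 0.4% of the time even when the routes are identical.

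**What the paired ratio would show.** The standard error of the mean ln ratio is √[σ²(1/2 + 1/4)/20], with σ² = ln(1 + CV²), and t(19) = 1.729. For a true ratio of 0.5, the typical 90% CI is 0.45–0.55 at CV 30% and 0.42–0.60 at CV 60%. If the ratio itself varies between subjects with an assumed ln-SD of 0.5, these widen to about 0.40–0.62 and 0.38–0.65.

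**Would AUC catch it?** A proportional halving of the whole profile gives an AUC ratio near 0.5 and fails 80–125%. If trough halves through faster elimination, a one-compartment steady-state model with a 336 h interval gives exp(k₂·336) = 2·exp(k₁·336) − 1. At the 75 h half-life in Protocol 1.3, k₁·336 = 3.105 and k₂·336 = 3.776, so the AUC ratio is 3.105/3.776 = 0.82; at 79 h it is also 0.82. A 90% CI around 0.82 may or may not fail.

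**The case against.** Much of the other side stands.

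- **The threshold is a reasoned choice.** Protocol 1.3 reports high receptor occupancy in over 90% of samples above 300 ng/mL, and no apparent association between concentration and viral load reduction in the Phase 3 study. A halving that stays above 300 ng/mL is not shown to be a wrong bridge decision, which is why the criterion should stay.
- **A reader might infer that the SAPs exclude any trough ratio or summary.** The text does not go that far. The unlabelled sentence in IM SAP 4.5 follows the trough paragraphs and could be read as covering trough, and the general methods sections of both SAPs promise summary statistics for continuous data. The gap is in the code and shells, with text too loose to close it.
- **A reader might infer that a halving would go wholly unseen.** It would not. Listings 16.2.5 (IM) and 16.2.5.2 (push) print every concentration with troughs flagged. The AUC criterion is a partial backstop and belongs to a primary objective for push, although only a secondary one for IM.
- **A reader might infer that TOST usually passes a halving.** That depends on high infusion shares. The documents report means above 30 µg/mL on infusion, but also about 20% of subjects below the effective concentration at Week 2, 63% above 0.3 µg/mL on IM, and a median of 0.23 µg/mL above 85 kg. None gives a 95% share.
- **Fisher's role differs.** IM SAP 4.5 bases the bridge on TOST and calls Fisher supporting evidence; Protocol 9.7 rests on Fisher.

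**Conclusion.** The point holds in limited form. A primary objective stated as a comparison of concentrations is analysed only as a count at 300 ng/mL, and no code or shell estimates the trough ratio for either route. That the trough criterion can be met at a true ratio of 0.5 is exact arithmetic. How often this would happen runs from about half of trials to none, depending on an infusion share that the documents do not fix and on assumed trough variability. The fall would be missed by the trough analysis, not by all the output. This is worth correcting because the ratio answers the stated objective from data already collected; it does not invalidate the 300 ng/mL rule.

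**What to change.** Keep the 300 ng/mL criterion. In IM SAP 4.5 and IV push SAP 4.4:

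1. Fit the same type of mixed model to ln(Ctrough). State which troughs enter and how the period term is coded for them: it is now defined only as PK Period 1 or 2 per route, while IM has four test-route doses against two infusions.
2. State a rule for troughs below the 0.010 µg/mL limit of quantitation (Protocol 7.2.7), for example half the limit, with a sensitivity check, since the choice matters on the log scale.
3. Name the parameter in the IM SAP 4.5 sentence on the ratio of geometric means.
4. Add the test/reference trough geometric mean ratio with 90% CI, and summary trough concentrations by route, to the trough tables. Label the ratio a supporting estimate and quote it with the bridge conclusion.

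The cost is SAP wording, extra table rows and one more analysis with its coding rules; no new subjects, visits or samples. The report may show a lower trough beside a passed threshold test, which would then need interpretation.

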**Notes Applicable to All Tables**

General Programming Notes:

1. The tables will be programmed to show aggregate data only.
2. Review the data prior to programming. Check the data for inconsistencies and anomalies. Report suspected data errors to the lead programmer who can determine if they should be addressed by DM.
3. Follow the Quality Control Plans (\\\Westat.com\dfs\CTWRKGRP\PUBLIC\Resources\DA\QC\_Plans) for Tables, Listings, and Graphs. Perform the quality checks, using the Checklist.
4. Always check the population totals. All subjects should be accounted for in all tables. A row for "Unknown" or "Missing" values can be added to any table as appropriate to account for all subjects.
5. For summary statistics: N should always be an integer; minimum and maximum should have the same number of significant digits as is present in the data; mean and median should be calculated to be one additional significant digit than the data collected; standard deviation should be calculated to be two additional significant digits than the data collected.
6. Percentages should be calculated to one decimal place. The true number of treated subjects, which appears at the top of columns in most tables should be calculated once in libnames.sas and put into macro variables to ensure consistency. This number should not be re-calculated when calculating percentages.
7. Follow the mocks, especially regarding details, such as titles, capitalization, order of columns and row labels, and footnotes. Standard table formatting may be followed, as some mocks may have been created due to space/pagination considerations. The visit names in the mocks are examples only. Consult the protocol and SAP and present all scheduled visits for the item in question.
8. Additional footnotes may be required to fully/more accurately describe the contents of a table (decided during development). Consult project leader and lead biostatistician with questions.

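### Trough bridge test: the analysis sentence pools readings against a per-subject criterion, and the relative-risk event and the deciding mean are left open

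*SAP*

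**What the plan says.** The SAP file holds two plans, one for the IM portion and one for IV push. In both, the bridge criterion is the proportion of subjects with mean (IV push: average) Ctrough at or above 300 ng/mL, comparable between routes. Protocol 9.7 and the mock tables (IM Tables 14.2.1 and 14.2.2, IV push Table 14.2.2) have the same unit and direction.

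The instructions that follow read differently:

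- **Unit.** IM SAP 4.5 pools all Ctrough "measurements into two groups (IVI=Reference; IMTest) and dichotomizing the" data. IV push SAP 4.4 does the same: "measurements into two groups (IVI=Reference; IVP=Test) and dichotomizing the".
- **Coding.** Both code below 300 as 1 and at-or-above 300 as 0.
- **Independence.** IM: "the PK bridge will be based on relative risk assuming that the binary data in the two infusion groups are independent samples". IV push: "assuming that the binary data in the two infusion groups are independent samples".
- **Code.** "proc freq data=<filename> order=data", then a relative-risk equivalence request with margins 0.80 and 1.25 and the Farrington-Manning method. No column option is given.
- **Mean.** For geometric and arithmetic mean Ctrough, the IM SAP says both "will be calculated and analysis results will be presented for both means". The IV push SAP says only average.
- **Fisher's test.** Protocol 9.7 and the synopsis judge comparability by Fisher's exact test. IM SAP 4.5 presents it as "additional supporting evidence for equality of binomial proportions between the two administrative routes", after basing the bridge on the relative risk.

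**The concern.** Trough concentration is the primary PK objective for the IM portion and one of two primary PK comparisons for IV push. Fisher's p-value does not depend on which category is coded 1, but a relative-risk equivalence test does. Nor is the test indifferent to whether the rows are 20 subjects or 80 repeated readings from those subjects. The criterion and the analysis sentence therefore describe different tests. In addition, two IM bridge tables with no stated primary leave the deciding mean to be chosen after results are seen, in an open-label study.

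**Working it through.** **Plan's own figure.** Protocol 9.8 claims 80% power with 20 subjects per route. It rests on clearance variability and AUC coefficients of variation. With a within-subject CV of 23% and an assumed true ratio of 1.00, a paired AUC test at n=20 has 82.3% power, so the figure reproduces for AUC. No power is stated for the trough test.

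**Test.** Farrington-Manning score test for p1/p2 (1 = new route, 2 = IVI), at R0 = 0.80 and R0 = 1.25:

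z = (p1 − R0·p2) / √[p̃1(1−p̃1)/n1 + R0²·p̃2(1−p̃2)/n2]

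Here p̃1 and p̃2 are the maximum-likelihood estimates under p1 = R0·p2. The overall p is the larger of the two one-sided p-values; a pass needs p < 0.05, matching the 90% limits.

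**1. Event (20 subjects per route).**

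- 19/20 v 19/20, event ≥300: numerator 0.95 − 0.80×0.95 = 0.19; SE 0.0976; z = 1.947; p = 0.026, pass.
- Same data, event <300 (1/20 v 1/20): numerator 0.01; SE 0.0616; z = 0.162; p = 0.44, fail.
- 20/20 v 20/20, event ≥300: 0.20/0.0894 = 2.236; p = 0.013, pass. On <300 it is 0/20 v 0/20; the variance is zero and the ratio is 0/0, so there is no result.

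Over all 21×21 outcomes, passes occur only at (18,18), (19,19), (19,20), (20,19) and (20,20) events. On <300 a pass would need at least 18 of 20 subjects below threshold on both routes. If the true ≥300 rate is 80% (assumed), that has probability 3.3×10⁻¹¹ on one route alone. Swapping rows does not change the verdict, because 0.80 = 1/1.25.

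**2. Unit (85% on both routes, event ≥300).** Four test doses and two on-study IVI doses in 20 subjects give up to 20×4 = 80 and 20×2 = 40 readings.

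| Data | Deciding z | p | Result |
|---|---|---|---|
| 17/20 v 17/20 subjects | 0.17/0.1143 = 1.488 | 0.068 | fail |
| 68/80 v 34/40 readings | −0.2125/0.0973 = −2.184 | 0.0145 | pass |
| 34/40 v 34/40 readings | 0.17/0.0808 = 2.104 | 0.018 | pass |

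**3. Type I error if readings are pooled.** Simulation at a true ratio of 0.80: 20 subjects, latent-normal model, 40,000 trials per cell. Rates and correlations are assumptions.

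| Troughs per subject (test + IVI) | Correlations | 80%/64% | 90%/72% | 95%/76% |
|---|---|---|---|---|
| 4+2 | within = cross, 0.8–0.9 | 3–4% | 7–9% | 11–14% |
| 2+2 | within = cross, 0.8–0.9 | 1.6–5.2% across all three rates (5.4% at most in a repeat run) | | |
| 2+2 | within 0.8–0.9, cross 0.6 | 3% | 5–6% | 6–7% |

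At subject level on ≥300 with independent routes, the exact sizes are 0.1%, 1.6% and 3.7%.

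Trough counts are also an assumption, because the SAP's time-point graphic is not available. Protocol 6.3 describes full sampling after two IVI and two IM doses (2+2); pre-dose samples on Days 43 and 57 would make it 4+2. Protocol 6.2 sampling days allow 4+2 in the Core Group, and Protocol 6.1 supports 2+2 in the Sentinel Group.

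**4. Deciding mean.** Troughs of 100 and 600 ng/mL have geometric mean √(100×600) = 245 and arithmetic mean 350. One such subject moves 18/20 v 18/20 (0.18/0.1061 = 1.697, p = 0.045, pass) to 17/20 v 18/20 (0.13/0.1079 = 1.205, p = 0.114, fail).

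**5. Fisher as the criterion.** IVI 20/20 v new route 16/20 gives two-sided Fisher p = 0.106, not significant. The equivalence test on the same table has numerator 0.80 − 0.80×1.00 = 0, so z = 0 and p = 0.50.

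**The case against.** The strongest reply is that the intended analysis is recoverable. The criterion sentence, Protocol 9.7 and three mock tables all refer to subjects at or above 300. Calculating two kinds of mean makes no sense if raw readings are dichotomised. The IV push mock title uses pooling for combining Sentinel and Core subjects. IM SAP 4.5 sends its outputs to the mocks, and programmers are told: "Follow the mocks, especially regarding details, such as titles, capitalization, order of columns and row labels, and footnotes". This stands as evidence of intent, and the reading-level interpretation is the weaker one. It does not settle the matter. The analysis sentence still refers to all the measurements, the mocks' programmer notes point back to the SAP code, and no mock specifies the relative-risk column or which mean decides.

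A reader might go further in three ways that the documents do not support:

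- **That the code tests below 300.** Coding below 300 as 1 does not itself contradict the criterion. With data-order sorting, the column order follows the input file, so the event is undetermined. The near-impossible pass in step 1 is what happens if below 300 is used, not what the code specifies.
- **That the code pools readings.** It works on counts and is neutral on the unit; only the text raises the question.
- **That ignoring the pairing of routes creates a false bridge.** The subject-level sizes in step 3 are all below 5% even with independent routes. A matched-pair test is not always better: 18/20 v 18/20 with two discordant subjects each way gives 0.051 against 0.045.

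**Conclusion.** The point holds as a specification fault on a primary PK endpoint and should be fixed before the analysis is run. The pooling sentence conflicts with the per-subject criterion, the relative-risk event is not fixed, and the deciding mean is not named. The verdict changes in steps 1, 2 and 4 are arithmetic on illustrative tables and need no assumption about correlation.

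Type I error inflation is conditional. It reaches about 7–9% and 11–14% only with pooled readings, 4+2 troughs, high assumed rates and correlations of 0.8–0.9. With the 2+2 count that the IM sampling text supports, it is about 1.6–5.2%, rising to about 6–7% only at the highest assumed rate with cross-route correlation 0.6. A general claim that the plan inflates type I error is not supported. The Fisher mismatch between Protocol and SAP also stands, because non-significance at n=20 does not show comparability.

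**What to change.** (a) In IM SAP 4.5 and IV push SAP 4.4, replace the pooling sentence with one binary value per subject per route: mean Ctrough at or above 300 ng/mL, yes or no. Name the mean that decides and make the other a sensitivity analysis.

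(b) Name at-or-above 300 as the event in the text. In PROC FREQ, set the RELRISK column and the row order explicitly, so that the ratio reads new route over IVI.

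(c) Align Protocol 9.7 and the synopsis with IM SAP 4.5: the relative-risk equivalence test decides and Fisher's test is supportive.

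A matched-pair analysis may be added as an optional sensitivity analysis. Subjects with data on only one route would drop out of it.

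The cost is a few lines of text and code in each SAP and one aligned statement in the Protocol and synopsis. No new data are needed, and (a) and (b) bring the text into line with the existing mock tables.
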